APPENDIX 1. CONTRACEPTIVE GUIDELINES

Women of childbearing potential, who are sexually active, must agree to the use of the following highly effective form of contraception throughout their participation during the study treatment and for 6 months after the last dose of study treatment(s):

- Progestogen-only hormonal contraception associated with inhibition of ovulation:
 - Oral
 - Injectable
 - Implantable
- Intrauterine device
- Intrauterine hormone-releasing system
- Bilateral tubal occlusion
- Vasectomized partner
- Sexual abstinence if it is the preferred and usual lifestyle of the patient

Partners of male patients can take combined (estrogen- and progestogen-containing) hormonal contraception associated with inhibition of ovulation:

- Oral route
- Intravaginal route
- Transdermal route

Male patients with female partners of reproductive potential must use effective contraception during treatment and for 6 months following the final dose of study treatment (Clinical Trials Facilitation and Coordination Group 2014).

APPENDIX 2. CONCOMITANT MEDICATIONS ASSOCIATED WITH A RISK OF QTC INTERVAL PROLONGATION AND/OR TORSADES DE POINTES

RP-6306 have not demonstrated adverse effects on QT prolongation in studies to date, however caution is advised when administering RP-6306 with any drug that may prolong QT.

A vast number of medications prolong the QT interval. They are preferably classified based on the degree of QT prolongation they induce. This is specifically medication dependent. For example, many commonly used medications, such as diphenhydramine and azithromycin, exhibit QT-prolonging effects. However, the degree of QT prolongation is not severe enough to warrant caution in healthy patients. These medications bind to the human ether-related gene (hERG) channels and reduce electrical conduction through the potassium ion channels. This results in delayed repolarization of the heart.

Caution is advised when combining QT-prolonging medications or when using these medications in patients with electrolyte abnormalities. Below is a list of potential medications that may prolong QT interval. Patients receiving medications classified as "know risk" should be excluded. Please reach out to the Medical Monitor prior to enrolling any patient on RP-6306 or starting them on new medication while on study that you believe may prolong QT. Additionally, consulting with your local pharmacist is advised.

Risk	Drug Categories				
	Antiarrhythmic Drugs	Common Antibacterial and Antifungal Drugs	Prokinetic and Antiemetic Drugs	Antipsychotics	Antidepressants
Known risk	Amiodarone Disopyramide Dofetilide Dronedarone Flecainide Ibutilide Procainamide Quinidine Sotalol	Moxifloxacin Levofloxacin Ciprofloxacin Clarithromycin Erythromycin Azithromycin Fluconazole Pentamidine	Domperidone Chlorpromazine Ondansetron Droperidol	Haloperidol Mesoridazine Thioridazine Pimozide	Escitalopram Citalopram
Possible risk		Telavancin Telithromycin Gemifloxacin Norfloxacin Ofloxacin	Dolasetron Granisetron Promethazine Tropisetron	Lithium Clozapine Paliperidone Risperidone Promethazine Perphenazine Pimavanserin Iloperidone Aripiprazole Asenapine	Clomipramine Desipramine Imipramine Mirtazapine Nortriptyline Trimipramine Venlafaxine
Conditional risk	Ivabradine	Amphotericin B Itraconazole Ketoconazole Metronidazole Posaconazole Voriconazole Cotrimoxazole (avoid in congenital long QT syndrome)	Metoclopramide	Quetiapine Olanzapine Ziprasidone	Amitriptyline Doxepin Fluoxetine Fluvoxamine Paroxetine Setraline Trazodone
Alternatives		Penicillin Cephalosporins Doxycycline Anidulafungin	Aprepitant Fosaprepitant Palonosetron	Brexpiprazole	Desvenlafaxine Bupropion (except in supratherapeutic dose) Vortioxetine Vilazodone Levomilnacipran Milnacipran

Note: Known risk of torsades de pointes (TdP): These drugs prolong the QT interval and are clearly associated with a known risk of TdP, even when taken as recommended and should be excluded. Possible risk of TdP: These drugs can cause QT prolongation but lack evidence for a risk of TdP when taken as recommended. Conditional risk of TdP: These drugs could cause TdP only under certain conditions, such as excessive dosing, electrolyte imbalance, and interacting with other drugs that can cause TdP. Alternatives: Drugs that at this point have not been linked to clinically significant QTc prolongation. (Please see http://crediblemeds.org for an exhaustive list.)
Ondansetron is only prohibited if administered as a single intravenous dose of >16 mg. Oral administration is allowed.

Source: Porta-Sanchez 2017

APPENDIX 3. STRONG CYP3A INHIBITORS AND INDUCERS

Strong CYP3A Inhibitors

Inhibitor	Therapeutic Class
Ritonavir	Protease inhibitors
Cobicistat (GS-9350)	None
Ketoconazole	Antifungals
Troleandomycin	Antibiotics
Telaprevir	Antivirals
Itraconazole	Antifungals
Indinavir	Protease inhibitors
Voriconazole	Antifungals
Mifepristone	Antiprogestins
Clarithromycin	Antibiotics
Posaconazole	Antifungals
Telithromycin	Antibiotics
Grapefruit juice	Food products
Ceritinib	Kinase inhibitors
Conivaptan	Diuretics
Nefazodone	Antidepressants
Nelfinavir	Protease inhibitors
Saquinavir	Protease inhibitors
Ribociclib	Kinase inhibitors
Idelalisib	Kinase inhibitors
Boceprevir	Antivirals

CYP3A=cytochrome P450 3A.

Strong CYP3A Inducers

Inducers	Therapeutic Class
Rifampin	Antibiotics
Mitotane	Other antineoplastics
Avasimibe	Other antilipemics
Rifapentine	Antibiotics

Inducers	Therapeutic Class
Apalutamide	Antiandrogens
Ivosidenib	Cancer treatments
Phenytoin	Anticonvulsants
Carbamazepine	Anticonvulsants
Enzalutamide	Antiandrogens
St John's Wort extract	Herbal medications
Lumacaftor	Cystic fibrosis treatments
Phenobarbital	Anticonvulsants

CYP3A=cytochrome P450 3A.

Sensitive CYP3A Substrates

Inducers	Therapeutic Class
Saquinavir	HIV antiviral
Indavir	HCV antiviral
Maraviroc	HIV antiviral
Lopinavir	HIV antiviral
Tipranavir	HIV antiviral
Darunavir	HIV antiviral
Efavirenz	HIV antiviral
Nelfinavir	HIV antiviral
Boceprevir	HCV antiviral
Daclatasvir	HCV antiviral
Velpatasvir	HCV antiviral
Telaprevir	HCV antiviral
Nevirapine	HIV antiviral
Sofosbuvir	HCV antiviral
Rilpivirine	HIV antiviral
Ritonavir	HCV antiviral
Estradiol	Oral contraceptive

CYP3A=cytochrome P450 3A; HCV=hepatitis C virus; HIV=human immunodeficiency virus.

APPENDIX 4. RESPONSE EVALUATION CRITERIA IN SOLID TUMORS, VERSION 1.1

Evaluation of Target Lesions

CR: Disappearance of all target lesions (TLs). Any pathological lymph nodes (whether target or nontarget) must have reduction in short axis to <10 mm.

PR: At least a 30% decrease in the sum of the diameters of TLs, taking as reference the baseline sum diameters.

PD: At least a 20% increase in the sum of the diameters of TLs, taking as reference the smallest sum on study (this includes the baseline sum if that is the smallest on study). In addition to the relative increase of 20%, the sum must also demonstrate an absolute increase of at least 5 mm. (Note: the appearance of one or more new lesions is also considered progressions).

Stable Disease (SD): Neither sufficient shrinkage to qualify for PR nor sufficient increase to qualify for PD, taking as reference the smallest sum diameters while on study.

Evaluation of NonTLs

CR: Disappearance of all nonTLs and normalization of tumor marker level. All lymph nodes must be nonpathological in size (<10 mm short axis).

Note: If tumor markers are initially above the upper normal limit, they must normalize for a patient to be considered in complete clinical response.

NonCR/NonPD: Persistence of one or more nonTLs and/or maintenance of tumor marker level above the normal limits.

PD: Appearance of one or more new lesions and/or unequivocal progression of existing nonTLs. Unequivocal progression should not normally trump TL status. It must be representative of overall disease status change, not a single lesion increase.

Although a clear progression of "nontarget" lesions only is exceptional, the opinion of the treating physician should prevail in such circumstances, and the progression status should be confirmed at a later time by the review panel (or Principal Investigator).

Evaluation of Best Objective Response

The best objective response (BOR) is the best response recorded from the start of the treatment until disease progression/recurrence (taking as reference for PD the smallest measurements recorded since the treatment started). The patient's best response assignment will depend on the achievement of both measurement and confirmation criteria.

For Patients With Measurable Disease (ie, Target Disease)

Target Lesions	Nontarget Lesions	New Lesions	Overall Response	Best Overall Response When Confirmation Is Required ^a
CR	CR	No	CR	>4 wks confirmation ^b
CR	NonCR/nonPD	No	PR	>4 wks confirmation ^b
CR	Not evaluated	No	PR	
PR	NonCR/nonPD/ not evaluated	No	PR	
SD	NonCR/nonPD/ not evaluated	No	SD	Documented at least once 8 wks from first dose of study treatment ^b
PD	Any	Yes or No	PD	No prior SD, PR, or CR
Any	PDc	Yes or No	PD	
Any	Any	Yes	PD	

CR=complete response; PD=progressive disease; PR=partial response; RECIST=Response Evaluation Criteria in Solid Tumors; SD=stable disease.

- ^a See RECIST v1.1 manuscript for further details on what is evidence of a new lesion (Eisenhauer 2009).
- b Only for nonrandomized studies with response as primary endpoint.

Note: Patients with a global deterioration of health status requiring discontinuation of treatment without objective evidence of disease progression at that time should be reported as "symptomatic deterioration." Every effort should be made to document the objective progression even after discontinuation of treatment.

For Patients With Nonmeasurable Disease (ie, Nontarget Disease)

Nontarget Lesions	New Lesions	Overall Response
CR	No	CR
NonCR/nonPD	No	NonCR/nonPD ^a
Not all evaluated	No	Not evaluated
Unequivocal PD	Yes or No	PD
Any	Yes	PD

CR=complete response; PD=progressive disease; SD=stable disease.

^c In exceptional circumstances, unequivocal progression in nontarget lesions may be accepted as disease progression.

[&]quot;NonCR/nonPD" is preferred over SD for nontarget disease since SD is increasingly used as an endpoint for assessment of efficacy in some studies so to assign this category when no lesions can be measured is not advised.

APPENDIX 5. EASTERN COOPERATIVE ONCOLOGY GROUP PERFORMANCE STATUS

Description	Grade
Fully active; able to carry on all pre-disease performance without restriction.	0
Restricted in physically strenuous activity, but ambulatory and able to carry out work of a light or sedentary nature (ie, light housework, office work).	1
Ambulatory and capable of all self-care but unable to carry out any work activities; up and about more than 50% of waking hours.	2
Capable of only limited self-care; confined to bed or chair more than 50% of waking hours.	3
Completely disabled; cannot carry on any self-care; totally confined to bed or chair.	4
Dead.	5

Source: Oken 1982

APPENDIX 6. SIMULATED OPERATING CHARACTERISTICS OF DOSE ESCALATION DESIGN

Table 22 shows the operating characteristics of the proposed design for this study with 5 scenarios involving various numbers and locations for the MTDs, based on 5000 simulations using the BOIN Design Desktop Program. The computer simulations allow operating characteristics of the design to be estimated, such as the expected proportion of patients who will be either under- or over-dosed, how accurately the true MTD will be identified and how many patients are expected to be exposed to each dose level. The proportion of patients over-dosed, defined as receiving a dose that had a true dose-limiting toxicity rate of >30%, ranged between 15.6% and 28.5% across all assumed dose-toxicity models. The operating characteristics also shows that the design selects one of the true MTD(s), if any, with high probability and allocates more patients to the dose levels with the dose-limiting toxicity rate closest to the target of 0.25.

Table 1: Operating Characteristics of the Drug Combination BOIN design

	Dose Level			Number of	% Early			
	1	2	3	4	5	6	Patients	Stopping
Scenario 2								
True DLT Rate	0.12	0.25	0.42	0.46	0.51	0.55		
Selection %	24.8	62.4	11.1	1.5	0.1	0.0		0.2
% Pts Treated	27.2	47.9	20.3	3.8	0.7	0.1	21.6	
Scenario 3								
True DLT Rate	0.04	0.12	0.25	0.43	0.53	0.63		
Selection %	1.2	30.9	57.2	10.0	0.6	0.0		0.0
% Pts Treated	7.6	36.2	37.8	15.5	2.7	0.3	24.1	
Scenario 4								
True DLT Rate	0.02	0.05	0.08	0.10	0.25	0.40		
Selection %	0.1	3.7	8.3	22.0	52.0	13.9		0.0
% Pts Treated	1.9	15.6	17.5	25.5	27.7	11.7	28.5	
Scenario 5								

True DLT Rate	0.02	0.04	0.06	0.09	0.11	0.25		
Selection %	0.1	2.0	4.4	9.5	24.2	59.9		0.0
% Pts Treated	1.5	14.4	16.5	18.0	25.1	24.5	27.9	

BOIN=Bayesian optimal interval; DLT=dose-limiting toxicity; Pts=patients.

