For the purpose of overdose control, doses j and higher levels will be eliminated from further consideration if $Pr(pj > 0.25 \mid data) > 0.95$ and at least 3 evaluable patients have been treated at dose level j, where pj is the true DLT rate of dose level j, j = 1, ..., 5. This posterior probability is evaluated based on the beta-binomial model yj | pj ~ binomial(pj) with pj ~ uniform(0, 1), where yj is the number of patients experienced DLT at dose level j. When the lowest dose is eliminated, stop the trial for

safety. When the lowest dose is eliminated, stop the trial for safety. The above dose escalation/de-escalation and elimination rule can be equivalently presented in Table B, which will be used to conduct the trial.

Table B provides information on the different dose decisions based on number of evaluable patients and the number of DLTs reported. Note, more than 6 patients may be exposed at a dose level to better define the MTD.

 Table B:
 Dose Escalation/De-escalation Rules for the BOIN Design

		Number of Evaluable Patients at Current Dose Level										
Action	1	2	3	4	5	6	7	8	9	10	11	12
↑ if number of DLT ≤	0	0	0	0	0	1	1	1	1	1	2	2
Stay current dose if number of DLT =	NA	NA	NA	1	1	NA	2	2	2	2	3	3
\downarrow if number of DLT \geq	1	1	1	2	2	2	3	3	3	3	4	4
Elim if number of DLT ≥	NA	NA	3	3	3	4	4	4	5	5	6	6

BOIN = Bayesian optimal interval; \(\geq = \text{increase}, \quad = \text{decrease}, \text{DLT} = \text{dose-limiting toxicity}, \\ \text{Elim=eliminate}, \text{NA} = \text{not applicable}, \text{dose cannot be eliminated until at least 3 patients have been treated}

Note: Number of DLT is the number of patients with at least 1 DLT. When none of the actions (ie, escalate, de-escalate or eliminate) is triggered, stay at the current dose for treating the next cohort of patients.

Dose finding starts at Dose Level 1. The steps to implement the BOIN design are described as follows:

- 1. Patients in the first cohort are treated at Dose Level 1. Dose decisions will depend on 2 or more evaluable patients completing the first 2 14-day treatment cycles.
- 2. To assign a dose to the next cohort of patients, conduct dose escalation/de-escalation according to the rule displayed in Table B. When using Table B, please note the following:
 - a. "Eliminate" means eliminate the current and higher doses from the trial to prevent treating any future patients at these doses because they are overly toxic.

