 - b. When we eliminate a dose, automatically de-escalate the dose to the next lower level. When the lowest dose is eliminated, stop the trial for safety. In this case, no dose should be selected as the MTD.
 - c. If none of the actions (i.e., escalation, de-escalation or elimination) is triggered, treat the new patients at the current dose.

- d. If the current dose is the lowest dose and the rule indicates dose de-escalation, treat the new patients at the lowest dose unless the number of DLTs reaches the elimination boundary, at which point terminate the trial for safety.
- e. If the current dose is the highest dose and the rule indicates dose escalation, treat the new patients at the highest dose.
- 3. Repeat Step 2 until the maximum sample size of 36 evaluable patients is reached or stop the trial early if the number of evaluable patients treated at the current dose ≥9 and the decision according to Table B is to stay at the current dose.

After the study is completed, results from all DLT evaluable patients, including the relevant backfill cohorts, will be included to assess the MTD. The dose for which the isotonic estimate of the toxicity rate is closest to and no higher than 30% will be selected as the MTD. This computation can be implemented by the shiny app "BOIN" available at http://www.trialdesign.org. The RP2D for RP-6306 and FOLFIRI will be based on discussion between the Investigators and the Sponsor and will be either the established MTD or a dose lower than MTD based on the totality of the safety, PK, pharmacodynamics, and preliminary efficacy.

Dose-Limiting Toxicity Criteria:

Toxicity will be assessed using the National Cancer Institute (NCI) Common Terminology Criteria for Adverse Events (CTCAE) version 5.0 unless otherwise specified. A toxicity will be considered dose-limiting if it occurs during the first 2 cycles (28 days), meets the predefined criteria for DLT, and is deemed at least possibly related to study treatment. If multiple toxicities occur, the most severe toxicity will be used in the assessment.

A DLT is defined as any of the TEAEs (a TEAE is any event that was not present prior to the initiation of study treatment or any event that worsens in either intensity or frequency following exposure to study treatment and for up to 30 days following the last dose of study treatment) listed below that is not clearly and incontrovertibly due to disease progression or extraneous causes.

DLTs will be defined as any of the following:

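### Appendix 6 puts minimum over-dosing at 15.6%, but its own table gives 11.7% in Scenario 4 and 0% in Scenario 5; the simulated MTD-selection rule is also not stated

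*Protocol*

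**What the plan says.** Protocol Appendix 6 reports operating characteristics "with 5 scenarios involving various numbers and locations for the MTDs, based on 5000 simulations using the BOIN Design Desktop Program". It defines over-dosing as "receiving a dose that had a true dose-limiting toxicity rate of >30%, ranged between 15.6% and 28.5% across all assumed dose-toxicity models". The table beneath lists, for each scenario, the true DLT rate, the selection percentage and the percentage of patients treated at six levels, followed by the mean number of patients. The supplied text shows Scenarios 2 to 5. The patients-treated row, ending with the mean sample size, reads "27.2 47.9 20.3 3.8 0.7 0.1 21.6" for Scenario 2 and "7.6 36.2 37.8 15.5 2.7 0.3 24.1" for Scenario 3.

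On choosing the MTD, the Protocol Synopsis (Maximum Tolerated Dose) and SAP Section 3.2.2 both say that the dose whose "isotonic estimate of the toxicity rate is closest to and no higher than 30% will be selected as the MTD". SAP Section 7 gives a different definition: the highest dose with a DLT rate below 25%. Appendix 6 does not say which selection rule was simulated.

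**The concern.** Appendix 6 is where a reader judges how many patients the design exposes to over-toxic doses and how often it finds the right one. A summary range said to hold across all models should contain every scenario in the table. Two of the four visible scenarios lie below its lower end.

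The selection percentages matter in a similar way. If they were produced under a different MTD rule from the one the protocol and SAP Section 3.2.2 prescribe, they describe a different procedure from the one that will be applied to the final data.

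**Working it through.** **Over-dosing, from the table alone.** For each scenario, add the percentage of patients treated over the levels whose true DLT rate exceeds 30%.

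| Scenario | Levels above 30% (true rates) | Sum | Over-dosed |
|---|---|---|---|
| 2 | 3–6 (0.42, 0.46, 0.51, 0.55) | 20.3 + 3.8 + 0.7 + 0.1 | 24.9% |
| 3 | 4–6 (0.43, 0.53, 0.63) | 15.5 + 2.7 + 0.3 | 18.5% |
| 4 | 6 (0.40) | 11.7 | 11.7% |
| 5 | none | – | 0% |

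The stated minimum of 15.6% is not reproduced. Rounding allows Scenario 4 at most 11.75%. Thresholds of >25%, ≥25%, >33% and >40%, and selection percentages in place of treated percentages, do not give 15.6% to 28.5% either. A further scenario can only lower a minimum, so Scenario 1 cannot repair it.

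**Selection rule, by simulation.** Inputs from the documents: boundaries 0.197 and 0.298, the elimination row of Table B, a maximum of 36 patients, and an early stop at 9 or more patients on a dose that would be kept. Two inputs are assumptions.

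- Start at table level 2. Level 1 receives only 0.019 × 28.5 = 0.54 patients per trial in Scenario 4 and 0.015 × 27.9 = 0.42 in Scenario 5, so it was not the simulated start.
- Cohorts of 3, which gave the best fit and satisfy the protocol's minimum of 2.

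These settings reproduce the printed design. Mean sample size is 21.5/24.1/28.5/27.8 in Scenarios 2/3/4/5, against 21.6/24.1/28.5/27.9 printed. Every patients-treated cell is within 0.3 points. With allocation matched, only the final selection rule is left to vary:

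| True-MTD selection, % | Sc. 2 | Sc. 3 | Sc. 4 | Sc. 5 |
|---|---|---|---|---|
| Printed | 62.4 | 57.2 | 52.0 | 59.9 |
| Cohorts of 3, closest to 25%, no cap | 61.9 | 56.5 | 52.1 | 59.1 |
| Cohorts of 3, 30% cap | 58.5 | 53.3 | 46.4 | 47.0 |
| Loss from cap | 3.4 | 3.2 | 5.7 | 12.1 |
| Cohorts of 2, no cap | 58.7 | 55.4 | 51.7 | 60.6 |
| Cohorts of 2, 30% cap | 56.1 | 53.1 | 47.5 | 54.8 |
| Loss from cap | 2.6 | 2.3 | 4.2 | 5.8 |

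The printed values come from 5000 runs and have a standard error of about 0.7 points; the simulated ones (40,000 runs) have about 0.25.

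Two further results separate the rules, both with cohorts of 3:

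- Scenario 5, selection of level 5: 24.2% printed, 24.7% without the cap, 35.9% with it.
- Scenario 2, level 1 or no dose: 24.8 + 0.2 = 25.0% printed, 25.5% without the cap, 30.3% with it. The cap would leave about 5% of trials with no dose, but printed selection plus early stopping already totals 100.1%.

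Reading the cap as closest to 25% subject to 30%, or as the highest estimate not above 30%, gave the same true-MTD selection to one decimal. Stopping only on a literal stay in Table B gives capped values of 58.8/53.1/46.2/46.6% with cohorts of 3, so the result does not turn on the stopping rule.

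The cap also has a benefit. With cohorts of 3, selection of an over-toxic dose falls from about 13% to about 9% in Scenario 4, and from about 10% to 8% in Scenario 3.

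**The case against.** The lower bound has no defence, but several stronger readings should be resisted.

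- **That the whole range is wrong.** No visible scenario exceeds 24.9%, so a reader might infer that 28.5% is an error too. Five scenarios are announced and Scenario 1 is not in the supplied text; it may supply that maximum. Both printed ends also occur in the Scenario 4 row as other quantities (15.6 as the share at level 2, 28.5 as the mean sample size). That may be coincidence and proves nothing.
- **That the trial will find the MTD up to 12 points less often than printed.** The simulation is a six-step ladder. The written design moves to one of two neighbouring combinations and includes relevant backfill DLTs in the final estimate. The 12 points are the worst scenario at one assumed cohort size; with cohorts of 2 the loss there is about 6. Some of the shortfall from print is not due to the cap: with cohorts of 2, Scenario 2 is already 62.4 − 58.7 = 3.7 points below print without it. Lower true-MTD selection is partly the price of avoiding toxic doses.
- **That the allocation sentence is also wrong.** The appendix says that the design "allocates more patients to the dose levels with the dose-limiting toxicity rate closest to the target of 0.25". In Scenario 5 the level at 0.25 receives 24.5% and the level at 0.11 receives 25.1%. That is 0.006 × 27.9 = 0.17 patients, and the sentence holds in the other three visible scenarios.
- **That the simulation started at the wrong dose.** The Synopsis says "Patients in the first cohort are treated at Dose Level 1" and defines the rates with "where pj is the true DLT rate of dose level j, j = 1, ..., 5", while the table has six levels. If table level 1 is a de-escalation level, the two agree.

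The full protocol body is not in the supplied text and may state the simulation settings. What stands is the arithmetic on the lower bound, and the inference about the cap at moderate confidence.

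**Conclusion.** The lower end of the over-dosing range is wrong as written. From the table it is 0%, or at most 11.7% if only scenarios containing a dose above 30% are counted, instead of 15.6%. This needs no assumption. The upper end is unverified, not refuted.

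The printed selection percentages fit an uncapped rule and do not fit the 30% cap of the Synopsis and SAP Section 3.2.2. This is an inference from a simulation match and is not stated in the text. It rests on a start at table level 2, cohorts of 3, a maximum of 36, a one-dimensional ladder and no backfill data. If it is right, the cap costs roughly 3 to 12 points of true-MTD selection with cohorts of 3 and 2 to 6 with cohorts of 2, with fewer over-toxic selections in return.

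Severity is minor. Table B and the dose decisions do not depend on this appendix, and the wrong bound makes the design look less safe than the visible scenarios show.

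**What to change.** Restate the over-dosing range from the full table, including Scenario 1. State in Appendix 6 which MTD-selection rule was simulated, together with the start level and cohort size if the protocol body does not already give them. These are text edits and cost almost nothing.

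If the simulated rule was uncapped, first reconcile the MTD definitions in the Synopsis, SAP Section 3.2.2 and SAP Section 7. Then re-run the selection percentages under the single rule that results, and report selection of over-toxic doses next to selection of the true MTD. That is a few hours of simulation, and some accuracy figures will probably look less favourable. If the simulation already used the written rule, saying so is enough.
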